The transcranial electrical stimulation intervention is considered the independent variable, which contains three different conditions or categories differentiated by the type of stimulation used. These conditions define the three groups of treatment:

- 1) Transcranial direct current stimulation (tDCS), which induces a continuous current over the left primary motor cortex (M1). Current intensity is set at 2mA and it is applied for 20 minutes, with ramp-up and ramp-down of 15 seconds at the beginning and end of the stimulation period.
- 2) Transcranial alternat current stimulation (tACS), which induces an alternant current over somatosensory cortical region. Current intensity is set at 10-Hz and it is applied for 20 minutes, with ramp-up and ramp-down of 15 seconds at the beginning and end of the stimulation period.
- 3) Sham stimulation, which acts as a placebo-control group. It uses the same montage as the previous ones, but it does not emit any kind of current. The position of electrodes will be similar to the previous conditions, but the current will be just activated during the ramp-up and ramp-down moments.

Chronic pain patients are randomly assigned to one of these groups, although the active stimulation conditions agglutinate the 80% of sample (40% tDCS; 40% tACS), whereas the control group contains by the remaining 20%.

As dependent variables, we consider the assessed clinical symptoms, mainly pain characteristics (including intensity, location, frequency, duration and daily interference caused by pain), fatigue, depression/anxiety, sleep quality, physical functioning and life quality, following the guidelines proposed by the *Initiative on Methods, Measurement, and Pain Assessment in Clinical Trials* (IMMPACT; Dworkin et al., 2005).

Besides, as far as we aim to assess the efficacy of tES techniques to restore the potential dysfunctions in processing and modulation of pain in patients, central biomarkers as Conditioned Pain Modulation (CPM), Temporal Summation of Second Pain (TSSP) and EEG are also included as dependant variables. Thus, we try to identify any change in these variables which could be attributable to the intervention.

The intervention and evaluation protocols are more in-depth defined in the following sections.

4. Sample and recruitment

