For planning the sample size for this research, we used Gpower (v.3.1.9.2) software. Sample size was estimated for repeated measures ANOVA with three groups (tDCS, tACS, Sham) and two measurements (pre-treatment vs. post-treatment). Statistical power (SP) was predetermined a priori with a value of SP=0.99 ($\alpha=0,01$) to increase the validity of the subsequent analysis and ensure that we do not miss any statistically significant result.

We based the calculation on the data extracted from the meta-analysis by Zortea et al. (2019), who reported a moderate effect size for reduction of pain levels ($F=0.68$) in chronic non-cancer pain patients using the tDCS montage stimulating M1. These results were obtained after comparing 380 patients receiving active tDCS versus 381 who were given Sham stimulation.

Assuming this moderate effect size and the rest of described parameters (SP=0,99), a total of 21 patients would be large enough to detect statistically significant changes in the whole sample. However, it cannot be ignored the non-despicable drop-out rates of this patient profile, corroborated by the own researchers in previous investigations. Besides, we are interested in assessing the effect size of the tDCS intervention among the different categories or types of chronic pain, just as defined by the ICD-11 (Treede et al., 2015), and that requires to create big enough comparable groups. For these reasons, we decided to recruit a larger number of participants, thus stablishing the sample size in 120 patients with refractory chronic pain.

Concerning this research, pain is defined as refractory, regardless of etiology, when it meets the two following conditions. First, multiple evidence-based biomedical therapies

used in a clinically appropriate and acceptable fashion have failed to reach treatment goals that may include adequate pain reduction and/or improvement in daily functioning or have resulted in intolerable adverse effects. Second, pain persists even after psychiatric disorders and psychosocial factors that could be influencing treatment outcomes have been assessed and appropriately addressed.

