Epidemiological studies have consistently reported higher prevalence rates of chronic pain syndromes among women, compared to men (Jiménez-Trujillo et al., 2019; Cimas et al., 2018). As we intend to create a feasible and useful tool for clinical practice, these gender differences must also be considered when designing the recruitment plan and deciding the sex distribution of the sample. As we aim to assess the influence of sex/gender in tDCS treatment efficacy and central pain modulation mechanisms, we will recruit both male and female patients, although the latter will represent about 70% of the total sample, in accordance with clinical reality; whereas males will represent at least the 30% of the selected patients, in order to improve and facilitate subsequent comparative analysis. The **inclusion criteria** applied for the selection of patients are the following:

- Suffering a chronic pain condition of non-cancer nature. Those patients who report chronic pain even after overcoming an oncological process are suitable to participate, but only if they have received the definitive medical discharge and have been free from radiotherapy/chemotherapy for at least twelve months.
- Adult subjects (18-65 years old).
- Subjects able to provide informed consent to participate in the study and to self-report pain.
- Existing chronic pain which reaches an intensity of at least 4 on a 0-10 Numeric Rating Scale (NRS) on average over the past 3 months prior to enrolment.
- Pain intensity of at least 5 on a 0-10 NRS over the week prior to enrolment.
- Diagnosis of pharmaco-resistance to analgesic drugs across the WHO ladder.

Participants are allowed to continue with their usual pharmacological regimen, but it must have been stable during the two months previous to the enrolment, and it must not suffer modifications during the whole research period. We will account for the potential effects of some drugs over the efficacy of tDCS/tACS treatment (McLaren et al., 2017), making a registry of patients pharmacological prescriptions to consider them in further

analysis. Rejecting patients who consume medicaments which can apparently interfere with tDCS/tACS effects would not be a well-balanced alternative and would result in a huge loss of participants, since some of these drugs are included as priority treatment for many chronic pain conditions. As far as the **exclusion criteria** are concerned, they are exposed below:

- Chronic pain derived from current cancer disease.

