The main quantitative statistical analyses to assess the efficacy of transcranial electrical stimulation techniques consist of ANOVA-tests of repeated measures with three groups. Time-measures for each of the above-mentioned endpoints are taken as intragroup variables (pre vs. post), whereas intergroup measures refer to the received stimulation or treatment (tDCS vs. tACS vs. Sham). Thus, both clinical variables (for example, pain intensity, fatigue, sleep quality, disease severity and interference) and potential biomarkers (including brain oscillatory activity registered by EEG, CPM and TSSP response) are considered as intragroup variables.

Those covariates which show a significant correlation with clinical outcomes will be also included in their correspondent ANOVA analysis. These potential covariates are basically age, self-perceived stress, social support, catastrophism and medication intake.

All these statistical analyses will be repeated in separated groups of patients, created in the basis of sex, type and duration of chronic pain, among other characteristics. The objective is to assess whether the clinical outcomes depend on sex or diagnosis, as each tES could be more effective for specific diseases.

CPM/TSSP response and EEG pattern observed before the tES application are also regarded as potential predictors of the treatment efficacy. Thus, the pre-treatment indexes of these biomarkers will be used as independent variables in *Linear regression models*, which includes the clinical improvement in each endpoint as dependent measure. The procedure will be repeated with *Logistic regression analysis* establishing the respondent vs. no-respondent categories as dichotomic variable.

For last, we will register and assess the percentage of dropouts with their respective motives, in order to obtain an index of the feasibility of home-based tES approach. Client

satisfaction index and caregiver interview will also include questions about the capability of participants to manage with tES devices, data which will be qualitatively analysed.

8. Chronogram

WORKING PLAN (WP)		3	6	9	12	15	18	21	24	27	30	33	36
TASK	\ MONTH												
WP1. Development and selection of assessment and monitoring tools for refractory chronic pain patients													
Task 1.1.	Review of the literature and identification of the most common and important variables used as outcomes in clinical trials with chronic pain population.												

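### The sample of 120 is not shown to give adequate groups by pain type or sex: sham has 24 patients (about 7 men), and separate subgroup analyses do not test whether the effect differs

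*Combined protocol and SAP*

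**What the plan says.** Section 4 (Sample and recruitment) describes a G*Power calculation for a three-group, two-measurement repeated-measures ANOVA with effect size 0.68, power 0.99 and alpha 0.01. It concludes that "a total of 21 patients would be large enough to detect statistically significant changes in the whole sample". Two reasons are then given for going higher. One is dropout, with no rate. The other is an interest in the size of the effect within ICD-11 pain types, and "that requires to create big enough comparable groups". The section ends the argument by "thus stablishing the sample size in 120 patients with refractory chronic pain". The number of types, their expected shares and a minimum per type are not given.

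Section 3 (Study design) allocates 40% to tDCS, 40% to tACS and 20% to sham. On method it says only that "Chronic pain patients are randomly assigned to one of these groups"; no stratification factor or blocking is named.

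Sex is specific objective H in section 2. Section 4 repeats it ("As we aim to assess the influence of sex/gender in tDCS treatment efficacy") and plans about 70% women and at least 30% men.

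Section 7 (Data analysis plan) says that "All these statistical analyses will be repeated in separated groups of patients", formed by sex, type and duration of pain and other characteristics. The stated aim is to learn whether outcomes depend on sex or diagnosis. No treatment-by-subgroup interaction is named.

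**The concern.** One of the two reasons for the enlarged sample is the size of the pain-type groups, yet nothing shows that 120 provides it. The comparison with sham is limited by the smallest arm, which holds a fifth of the patients and is divided again in each subgroup analysis.

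The method also does not match the question. A significant result in one subgroup beside a non-significant result in another is not evidence that the effects differ. Repeated over many endpoints and several subgroup factors, separate tests invite claims that a technique works in one diagnosis and not in another, which small sham groups can produce by chance.

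**Working it through.** **The plan's own figure.** For the group-by-time interaction with k = 3 groups and m = 2 measurements, the noncentrality is f² × N × m / (1 − rho), with (k − 1)(m − 1) and (N − k)(m − 1) degrees of freedom. The plan states neither the correlation nor the group sizes used; rho = 0.5 and equal groups are assumed here. With f = 0.68 and N = 21 the noncentrality is 0.4624 × 21 × 2 / 0.5 = 38.8, and power at alpha 0.01 is 0.994. Twenty-one is the smallest multiple of 3 that reaches 0.99, so the figure is reproduced. The step from 21 to 120 has no formula to reproduce.

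**Sham counts (no effect size needed).**
- All: 120 × 0.20 = 24, against 48 in each active arm.
- Women: 24 × 0.70 = 16.8. Men: 24 × 0.30 = 7.2.
- Equal pain types (an assumption): 24/3 = 8, 24/5 = 4.8, 24/7 = 3.4.
- A type needs 10/24 = 42% of the sample to expect 10 sham patients.
- Dropout of 10%, 20% or 30% (assumed) leaves about 15, 13 or 12 sham women and 6.5, 5.8 or 5.0 sham men.

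**Chance spread without stratification.** The number of men on sham is hypergeometric (120 patients, 36 men, 24 sham): mean 7.2, 95% range 3 to 11, probability of 4 or fewer 0.086. For women the range is 13 to 21, and the probability of 9 or fewer is 0.0002.

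**Power, reading 0.68 as a standardised mean difference.** This is a two-sided, unadjusted two-sample t-test of one active arm against sham, with noncentrality 0.68 × √(n1 × n2 / (n1 + n2)).

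| Group | Active v sham | Noncentrality | Power, alpha 0.05 | Power, alpha 0.01 |
|---|---|---|---|---|
| All | 48 v 24 | 2.72 | 0.77 | 0.53 |
| Women | 34 v 17 | 2.29 | 0.61 | 0.36 |
| Men | 14 v 7 | 1.47 | 0.29 | 0.11 |
| One of 3 types | 16 v 8 | 1.57 | 0.32 | 0.13 |
| One of 5 types | 9.6 v 4.8 | 1.22 | 0.20 | 0.07 |
| One of 7 types | 6.9 v 3.4 | 1.03 | 0.15 | 0.04 |

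**Power in the plan's three-group ANOVA (alpha 0.01, same formula and assumptions as above).**
- f = 0.68: near 1 in 36 men; 0.96 in 17 patients (one of seven equal types).
- f = 0.34: 0.82 in 36 patients; 0.42 in 20. The whole-sample requirement becomes 66 instead of 21.

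The value 0.34 is 0.68/2, the conversion from a standardised difference for two equal groups. It is shown as a middle case.

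**Sex-by-treatment interaction (normal approximation).** For one active arm against sham, the standard error in SD units is √(1/16.8 + 1/33.6 + 1/7.2 + 1/14.4) = 0.546. If the effect differs between the sexes by 0.68 SD, 0.68/0.546 − 1.96 = −0.71, which gives power of about 0.24 at alpha 0.05. With counts rounded to 17, 34, 7 and 14 it is 0.23, and 80% power needs a difference of about 1.54 SD.

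**The case against.** The strongest reply is that, on the plan's own inputs, the subgroups are not short of power. With f = 0.68 and 21 patients per group, 120 covers five equal pain types (5 × 21 = 105), though not six (126), before dropout. The t-test figures drop the third arm and the pre-treatment measure. Adjusting for a baseline correlated 0.7 with outcome (assumed) would raise power at alpha 0.05 from 0.32 to 0.56 for 16 v 8, and from 0.29 to 0.50 for 14 v 7. This stands: low subgroup power follows from one reading of 0.68 and is not established by the documents. That reading is plausible, because section 4 calls 0.68 moderate and takes it from a two-group comparison of 380 active with 381 sham patients, but section 4 uses it as f.

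A reader might also infer that every subgroup analysis has a single-figure sham group. The documents do not support that. Women would have about 17 sham patients, an even two-way split by duration about 12, and a pain type with 42% or more of the sample at least 10.

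Section 4 speaks of interest in the effect size by type, which is estimation and not a promise of powered tests. That softens the purpose. It does not supply the missing group sizes, and section 7 still plans repeated tests.

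Finally, the absence of stratification is inferred from silence. The documents describe no randomisation method, so the 3-to-11 range applies only if the list is in fact unstratified.

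**Conclusion.** The point holds in a limited form. The part of the justification that rests on pain-type groups has no calculation behind it, and the separate analyses in section 7 do not answer the question they are set. Neither conclusion depends on an effect size.

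The sham count for men (about 7) follows from the planned shares. The counts per pain type (about 8, 5 or 3) rest on an assumed number of equal types.

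It would go too far to say that 120 is underpowered for subgroups: power in men runs from 0.11 to near 1 at alpha 0.01, depending on the reading of 0.68 and the analysis. The sex-by-treatment interaction, which is what the sex aim needs, has power of about 0.24 for a 0.68 SD difference in effects at alpha 0.05, in an unadjusted comparison of one active arm with sham.

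This should be changed, but it does not threaten the whole-sample primary comparison.

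**What to change.** 1. **Section 7.** Replace the tests in separate groups with treatment-by-sex and treatment-by-pain-type interaction estimates with confidence intervals, labelled exploratory. In the repeated-measures model these are the terms in which the group-by-time effect varies with sex or type.
2. **Section 4.** State that 120 is not shown to give adequately sized groups per pain type.
3. **Section 3.** Stratify randomisation by sex, in permuted 2:2:1 blocks of 5 or 10. With blocks of 5, 36 men make seven full blocks and one further patient, so 7 or 8 men would be on sham instead of a chance 3 to 11.

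Stratification balances sham within each sex. It does not raise the expected number on sham, and it does nothing for pain type.

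The cost is a less favourable justification of the sample size and a slightly more complex randomisation list. The sample size does not increase.

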6.1. Evaluation phases

Regarding the evaluation protocol, pre-treatment assessment is divided in two different sessions, separated by two weeks.

After obtaining their contact number from physicians, researchers maintain a first phone talk with the proposed participants to ensure they not comply with any exclusion criterion. During this brief interview, the first meeting with patients is also scheduled, according to their availability.

The first face-to-face session is intended to initiate the pre-evaluation process and it takes place fifteen days before starting the treatment. After signing the informed consent, participants will complete an exhaustive assessment protocol which includes an interview about their health status and clinical history, a set of quantitative sensory tests (Pain thresholds, CPM, TSSP) and some other questionnaires to assess psychosocial variables.

From this point to the end of the post-treatment evaluation, patients are required to complete a daily online survey about their symptoms and health condition. Moreover, patients will be given a wristband actigraph which should wear during the whole research period (except follow-up), in order to monitor their physical activity and sleep patterns.

The next evaluation will take place two weeks after the first one. During this period, participants are required to complete a daily online survey about their symptoms and health condition. Moreover, they are given a wristband actigraph which allows to monitor their physical activity and sleep patterns.

At the second session, patients will complete electroencephalographic records in different conditions and tasks, some of which include painful stimuli. Furthermore, we will collect additional clinical features through validated questionnaires and may also repeat the quantitative sensory testing. Caregivers of chronic pain patients will also be invited to this appointment to maintain an interview with researchers, which aims to determine their health status and the stress-related to the caring tasks.

Finally, researchers will give the participants the portable stimulator to apply the tDCS/tACS treatment, with the properly explanations about its functioning. It is planned to make a training stimulation session during this visit to ensure that patients are able to

connect and manage the device; researchers will also be available to make a video-call to assist the participant in the first stimulation session.

After completing the treatment period, participants are summoned to other two evaluation sessions with the same structure and assessment tools as in pre-treatment phase; in case of the daily measurements, the comparison is made between the average of the pre-treatment period and that of the post-treatment period. Therefore, differences observed between these two time-measurements are considered as index of the treatment efficacy. At the post-evaluation session, participants will also answer some questions about the satisfaction with the treatment and self-perceived usefulness/improvement.

Finally, in order to assess the long-term improvement derived from tES, we will contact participants by phone in order to invite them to a follow-up session six months after finishing the treatment. All questionnaires and sensory tests will be applied in the same way, except for daily numerical rating scale. Differences between these results and those obtained in pre-evaluation and post-evaluation will be analysed.

6.2. Evaluation methods and assessment tools

The following section provides a more in-depth description about the methodology used to evaluate the patients and their characteristics. The assessment process includes a compendium of questionnaires about clinical and psychosocial characteristics, several quantitative sensory tests and EEG records in diverse conditions.

Regarding the first face-to-face session, we collect relevant sociodemographic data to characterize the sample (e.g., sex, age, occupation, dependency certificate), which does not enable to know the personal identity. The interviewers also inquire about medication and lifestyle questions, such as smoking, alcohol consumption, drug use and physical activity. Patients may also be requested to execute some short physical tasks (for example, *Stais Climb Test*) to obtain a performance-based index of their physical function (Dobson et al., 2013). We also question about the type and onset of chronic pain, and whether he/she has been diagnosed with other relevant medical or psychiatric conditions.

Clinical features and health condition are assessed using the translated version of reliable and validated questionnaires for Spanish chronic pain population. At this initial stage, we focus on assessing relatively stable measures:

- Multidimensional Pain Inventory (MPI; Kerns et al., 1985; Pastor et al., 1995). It serves as a general index about the severity of the disease by asking for pain intensity, daily interference, self-perceived control over pain and perceived support from significant others.
- Short Form Health Survey SF-36 (Vilagut et al. 2005). World widely used, this questionnaire provides a complete picture of the participant health state, including subscales about vitality, mental health and physical, emotional and social functioning, among others.

We will also perform the quantitative sensory testing, which consists of the pain thresholds and the above-mentioned procedures to assess abnormalities in endogenous modulatory pain mechanisms, namely Conditioned Pain Modulation (CPM) and Temporal Summation (TSSP).

Pain thresholds are defined as the minimum intensity which must reach a stimulus to become in painful, as perceived and reported by the own person. Pressure pain threshold will be calculated using a digital handheld algometer (Wager Force One Model) which puts progressively heavier pressure over the skin surface. Heat pain threshold is obtained with a computerized thermal stimulator which progressively enhances the temperature of the skin with a small contact metal plate. In both cases, pressure and temperature increases to a constant pre-fixed rate, until the participant press a button to indicate she/he starts to feel pain. Pressure pain threshold is measured in kPa, whereas heat pain threshold is established as the temperature in degrees Celsius.

Although the specific CPM and TSSP protocols are not completely defined yet, we count with a wide catalogue of usually used instruments and equipment to perform these tests (Fernandes et al., 2019; O'Brien et al., 2018)

Conditioned Pain Modulation requires of two different painful stimuli applied in heterotopic body areas; thus, the conditioning stimuli (CS), tonic in nature, reduces the pain sensations from the phasic test stimuli (TS). As CS, we will use the ischemic pain produced by pressure cuff and/or the cold pressor test, which means the participant have to immerse their non-dominant hand into cold water. Regarding TS, we opt for the same procedures as to calculate the pain thresholds (i.e., digital handheld algometer and thermal stimulator), given that we aim to compare these isolated thresholds with those obtained

while the CS is present. The difference between these two measures is established as the CPM index.

Tentatively, Temporal Summation of Second Pain (TSSP) will be evoked with the thermal stimulator. After establishing the parameters which corresponds to a medium pain level (5/10 NRS) for each participant, it will be applied ten repetitive pulses with that temperature over the skin, separated by two and a half seconds. Patients have to rate the pain intensity which produces the first, fifth and last stimuli. The difference in pain intensity between the first and last pulse is established as the TSSP index.

Finally, we will explain the daily assessment plan to patients, which starts at this point (i.e., fifteen days before the treatment onset) and continues until fifteen days after the stimulation sessions have finished. Every day during this period, participants will be requested to complete a brief online survey to track the intensity of their symptoms and obtain a more reliable measure. These questionnaires will be sent to patients by phone message, after getting permission from participants.

Specifically, the daily survey consists of several Numerical Rating Scales (NRS) of eleven points (0-10) which ask about the intensity and unpleasantness of pain, interference, fatigue and medication usage, among others. During treatment period, participants can also report any side effect of stimulation through these questionnaires. For each symptom, we will obtain an average of measures obtained before starting the treatment, other average with measures during the treatment and one last average for post-treatment phase (e.g., fifteen days after finishing the intervention).

Moreover, patients will be given a wristband actigraph which should wear during the whole research period. These devices are capable of detecting the sedentary and activity bouts, as well as the intensity of these last ones, the raw acceleration and the distance walked every day. Besides, actigraphs can also measure the total sleep time, the sleep latency and the awakenings after sleep onset. Thanks to this actigraphy technology, physical functioning and sleep patterns will be effectively daily evaluated.

Thus, by the day of the second evaluation session, we will have already obtained a set of daily measures whose average will serve as a reliable clinical baseline. In this second appointment, as part of the potential biomarkers of chronic pain, we will register the electroencephalography (EEG) of the patients during various conditions (Davis et al., 2017). Firstly, EEG will be assessed during a resting state to capture spontaneous brain

activity, the spectral power of the oscillations and inter-site phase connectivity (Ploner et al., 2017). Secondly, we will analyse wave components of the contact heat evoked potentials (CHEPs) to obtain a neural correlate of the painful stimuli processing. For last, in order to study the modulatory role of attention in pain perception, we propose to obtain the evoked potential derived from a TSSP protocol, both paying exclusive attention to pain and during a simple cognitive task.

Besides, we will repeat the same procedure of quantitative sensory testing to ascertain its reliability. Finally, the following questionnaires will be used to get an accurate measure of some key symptoms and problems which usually accompanies chronic pain:

- Hospital Anxiety and Depression Scale (HADS; Cabrera et al., 2015). It represents a really useful tool to assess mood state and screen for depressive or anxiety disorders, which frequently cooccurs with chronic pain.
- Modified Fatigue Impact Scale (MFIS; Duarte et al., 2017; Kos et al., 2005), which accounts for the physical, emotional and social components of fatigue. Fatigue usually accompanies chronic pain conditions and results in great limitations for the daily functioning of patients.
- Pittsburgh Sleep Quality Index (PSQI; Macías & Royuela, 1996). This inventory inquiries into several areas about the sleep patterns, such as the related disorders, the self-perceived quality or the time passed until falling asleep.
- Zarit Burden Interview (Martín et al., 1996). This instrument is used with the principal caregivers of the patients to assess the stress and negative feelings associated with the caring tasks. Thus, it represents the core of the evaluation protocol for caregiver, and it intends to pay attention to this figure but also to add information about the patient autonomy.

In sum, all the proposed questionnaires assess relevant clinical variables which are expected to be improved by tES treatment. Therefore, changes observed in them between pre- and post-evaluation will be subjected to statistical analysis and taken as efficacy indices of treatment.

However, there are some other variables which, despite not expecting to be modified, could influence the treatment outcomes for better or worse. We refer to social support, self-perceived stress, catastrophizing thinking and beliefs about controllability of pain

(Adams & Turk, 2015; Keefe et al., 2004; Jensen et al., 2011). Thus, these factors must be taken into account when assessing the efficacy of tES intervention and we intend to account them as covariates in statistical analysis.

Changes observed in criteria variables between pre- and post-evaluation must be equal or higher than the 30%, in order to ensure their clinical significance. It means that the improvement observed in self-reported questionnaires and in sensory testing (except for EEG) have to achieve or surpass the 30% of the original outcome. The direction of these differences depends on the specific scale; for example, it is expected a reduction in the global MPI score after treatment, but also a rise in pain thresholds. In the case of EEG, the analysis pre-post treatment are only subjected to the statistical significance. However, changes in brain activity patterns attributed to the tES will be tried to relate with improvement in clinical features.

Although all explained measurements are considered as success criteria of treatment, we selected pain intensity as the primary end point, taken as the average obtained from daily numerical rating scale. In this sense, participants will be classified into responders when they report, at least, a 30% decrease in their pain intensity. The rest of the variables are taken as secondary end points and are also regarded as treatment-efficacy indexes, basically the pain thresholds, life quality, physical functioning, interference caused by pain, pain unpleasantness, sleep quality, depression/anxiety, fatigue, caregiver burden and CPM/TSSP responses.

Table 1: End points of the clinical trial and their respective evaluation instruments

End points		Assessment tools
Primary end point	Pain intensity	Numerical Rating Scale of eleven points (0-10 NRS). Average obtained from daily self-reports during the fifteen days before treatment and the fifteen days after treatment.
Secondary end points	Global severity of chronic pain syndrome	Global and subscales scores of Multidimensional Pain Inventory (MPI).
	Interference caused by pain in daily living	Subscale score of Multidimensional Pain Inventory (MPI). Numerical Rating Scale of eleven points (0-10 NRS). Average obtained from daily self-reports during the fifteen days before treatment and the fifteen days after treatment.
	Pain thresholds	Pressure pain threshold using a digital handheld algometer, measured in kPa. Heat pain threshold using thermal stimulator, measured in degrees Celsius.
	Life quality	Short Form Health Survey SF-36
	Physical functioning	Daily recorded physical activity using actigraphy technology. Subscales scores of Multidimensional Pain Inventory (MPI)
	Sleep quality	Pittsburgh Sleep Quality Index (PSQI)

	Daily recorded sleep quality using actigraphy technology.
Pain unpleasantness	Numerical Rating Scale of eleven points (0-10 NRS). Average obtained from daily self-reports during the fifteen days before treatment and the fifteen days after treatment.
Mood and emotional functioning	Hospital Anxiety and Depression Scale (HADS) Numerical Rating Scale of eleven points (0-10 NRS) for assessing daily anxiety. Average obtained from daily self-reports during the fifteen days before treatment and the fifteen days after treatment.
Fatigue	Modified Fatigue Impact Scale (MFIS) Numerical Rating Scale of eleven points (0-10 NRS). Average obtained from daily self-reports during the fifteen days before treatment and the fifteen days after treatment.
Caregiver burden	Zarit Burden Interview (ZBI) applied to the identified reference person in charge of caring the patient
Endogenous pain inhibition response	Score obtained from Conditioned Pain Modulation (CPM) procedure
Endogenous pain facilitation response	Score obtained from Temporal Summation of Second Pain (TSSP) procedure

	Global satisfaction with treatment and self-perceived improvement	Ad-hoc designed questionnaire
--	---	--------------------------------------

7. Data analysis plan

First of all, we will perform reliability analysis on sensory measures, such as pain thresholds, CPM and TSSP magnitudes. The Intraclass Correlation Coefficient to establish the degree of association and agreement among the two scores obtained for each test.

After applying the pertinent filters to EEG records and once the descriptive analyses of the sample have been done, we will observe the correlation of the CPM/TSSP response and the EEG registry with the clinical features of the sample, taking into account just the pre-treatment evaluation. In order to reinforce the results, we may add *Linear regression analysis* to verify whether the dysfunctions in central modulatory mechanisms and brain processing of painful stimulus (CPM, TSSP, EEG) can act as predictors of the symptoms severity of chronic pain patients.

Besides, we will conduct simple ANOVA analyses to compare these indexes of pain processing and modulation (CPM, TSSP, EEG) between specific groups of patients, divided by type/origin of chronic pain and sex. We reserve the possibility of making *Cluster analyses* in the basis of the mentioned central biomarkers, following by an ANOVA comparison of clinical features between the emerged groups.

Besides, participants will be classified into CPM and TSSP respondents or non-respondents taking into account their results in these sensory tests. Those patients who report a significant increment in pain thresholds will be considered respondents; whereas the opposite applies for TSSP, as it must be detected a significant increase in perceived pain intensity in the last pulse compared to the first one. Depending on the proportions observed, it could be useful to divide TSSP respondents based on the degree of the pain sensitization. Regarding this sample division, we can compare the clinical profile of respondents and non-respondents patients using *Chi square statistic*.

As far as intervention efficacy is concerned, qualitative analyses will focus on differentiating the patients who effectively respond to treatment (Treatment-respondents) from those who do not improve (Non-treatment-respondent). Respondents are those

participants whose improvement in a certain clinical variable are equal or higher than the 30%; whereas non-respondents are all those who do not comply with this criterion. This variation is extracted from the comparison of pre- and post-treatment measurements.

Therefore, for each of the endpoints, we will obtain a number/percentage of respondents and non-respondents. Using the *Chi-square test*, we will compare the proportion of respondents between treatment groups to identify the most efficacious stimulation procedure. A separated analysis will be done for each described endpoint, which define what a respondent is.

The main quantitative statistical analyses to assess the efficacy of transcranial electrical stimulation techniques consist of ANOVA-tests of repeated measures with three groups. Time-measures for each of the above-mentioned endpoints are taken as intragroup variables (pre vs. post), whereas intergroup measures refer to the received stimulation or treatment (tDCS vs. tACS vs. Sham). Thus, both clinical variables (for example, pain intensity, fatigue, sleep quality, disease severity and interference) and potential biomarkers (including brain oscillatory activity registered by EEG, CPM and TSSP response) are considered as intragroup variables.

Those covariates which show a significant correlation with clinical outcomes will be also included in their correspondent ANOVA analysis. These potential covariates are basically age, self-perceived stress, social support, catastrophism and medication intake.

All these statistical analyses will be repeated in separated groups of patients, created in the basis of sex, type and duration of chronic pain, among other characteristics. The objective is to assess whether the clinical outcomes depend on sex or diagnosis, as each tES could be more effective for specific diseases.

CPM/TSSP response and EEG pattern observed before the tES application are also regarded as potential predictors of the treatment efficacy. Thus, the pre-treatment indexes of these biomarkers will be used as independent variables in *Linear regression models*, which includes the clinical improvement in each endpoint as dependent measure. The procedure will be repeated with *Logistic regression analysis* establishing the respondent vs. no-respondent categories as dichotomic variable.

For last, we will register and assess the percentage of dropouts with their respective motives, in order to obtain an index of the feasibility of home-based tES approach. Client

satisfaction index and caregiver interview will also include questions about the capability of participants to manage with tES devices, data which will be qualitatively analysed.

8. Chronogram

WORKING PLAN (WP)		3	6	9	12	15	18	21	24	27	30	33	36
TASK	\ MONTH												
WP1. Development and selection of assessment and monitoring tools for refractory chronic pain patients													
Task 1.1.	Review of the literature and identification of the most common and important variables used as outcomes in clinical trials with chronic pain population.												
